3.7.3. Rechallenge

If a study drug is stopped due to concomitant illness or other considerations, every attempt will be made to restart it, whenever possible. , Generally, rechallenge of subjects with significant AT elevations (>5xULN) should not be attempted..To maximize the adherence to the assigned therapy, any participant who decides to withdraw will initially be asked to attend follow-up visits, and at a later time to consider going back on his or her allocated therapy. Regardless of whether or not a participant has discontinued study drug every attempt will be made to ensure that he/she attends all follow-up visits and that all events are reported.

3.8. Participant Discontinuation from the study treatment

An excessive rate of participant discontinuations from either treatment or “drop-outs” from the study may render the trial non-interpretable. In this study, HbA1C data are crucial to the primary analysis and must be collected until the end of the study, even if participants are no longer taking study medication. Therefore, all efforts will be taken to

motivate participants to comply with all study procedures and to continue to be followed until the end of the trial.

Participants should be specifically asked about any possible AE or other reasons that led to their decision to withdraw from the study, and all AE information obtained should be recorded. Participants may withdraw their informed consent orally or in writing, and they are advised to withdraw informed consent in writing

The investigator and participant must discuss and determine further follow-up options. Options for follow-up are listed below, in descending order of preference:

1. Participant continues the regular study clinic visits at the investigator's site as outlined in the protocol.
2. Participant will be contacted by phone at the regular follow-up intervals.
3. Participant allows his/her general practitioner or a family relative to be contacted at the regular follow-up interval.
4. Participant will be contacted once at the end of the study.
5. Participant withdraws consent. This will be the last option and means that the participant does not agree to any kind of follow-up and specifically refuses any further contact with the investigator. This should happen only in exceptional cases. If possible by local regulations, this decision will be provided in writing. Vital status will be obtained at study end through public information according to local guidelines and as allowed by local regulations. For participants who do not agree to attend regular study visits, the investigator will encourage the participant to return to the clinic for at least one final visit in order to perform all assessments as outlined for the end of Study(EOS) visit.

3.9 Lost to Follow up

We define loss to follow-up as incomplete ascertainment of the primary outcome for participants randomized in the trial.

All attempts will be made to find all participants.

The following actions must be taken if a participant fails to return to the clinic for a required study visit:

- The site must attempt to contact the participant and reschedule the missed visit as soon as possible and counsel

the participant on the importance of maintaining the assigned visit schedule and ascertain whether or not the participant wishes to and/or should continue in the study.

- Before a participant is deemed lost to follow up, the investigator or designee must make every effort to regain contact with the participant (where possible, 3 telephone calls and, if necessary, a certified letter to the participant’s last known mailing address or local equivalent methods). These contact attempts should be documented in the participant’s medical record.

- If all attempts fail, depending on local legislation, death or other registries may be accessed or private investigation to locate a participant may be initiated.

- All randomly enrolled cases, no matter whether they fall off or not, should be recorded and retained, which can be kept as a file. It can also be used as the original record of Intention-To-Treat (ITT) analysis data.

4 STUDY PLAN AND TIMING OF PROCEDURES

4.1 Study Plan

Table 1 Study plan

		Screening	Rando misatio n	Treatment Phase		
Visits		Visit 0	Visit 1	Visit 2	Visit 3	Visit 4
Timelines(week)		-1	0	4	12	24
Treatment Days		7 +3	0	29 ±7	85 ±7	169 ±7
Informed Consent signed		×				
Eligibility criteria		×	×			
General information	Demographics		×			
	Medical History		×			
	Physical examination		×	×	×	×

Medications	Concomitant medications		×	×	×	×
Clinical assessment	Serum lipids (TG/non HDL-C/TC/LDL-C)		×	×	×	×
	HbA1c		×		×	×
	Plasma Glucose (PG), insulin, C-peptide levels at fasting and 2 h after drinking glucose solution(75g glucose)		×	×	×	×
	Hepatic function (Bilirubin, albumin, liver enzymes)		×	×		×
	Creatine kinase (CK)		×	×		×
	Renal function (Serum creatinine, BUN ,eGFR)		×	×		×
	Routine blood test		×			×
	Pregnancy test (HCG test for women of childbearing potential only)		×			
	ECG		×			×
	Adverse events		×	×	×	×
Questionnaire	IPAQ		×	×	×	×
Other work	Distributing study drugs		×	×	×	
	Patient medication guidance		×	×	×	
	Patient lifestyle guidance	×	×	×	×	×
	Patient diary dispensance	×	×	×	×	×
	Drug accountability log cards		×	×	×	×
	Retrieving drugs			×	×	×

4.2 Study procedure

This study consisted 2 periods: Screening and Open-label treatment

4.2.1 Screening period (Visit 0):

1. Informed Consent signed : participants should be fully notified before signing informed consent form. Investigator should also sign the informed consent form, copy of informed consent will give patient
2. Patient diary: Patients with eligible laboratory test results will record their daily diet, physical activity, and concomitant medication on the patient diary for one week. The patient records the regime 5 days per week, will be defined as good patient compliance and candidate subject.

4.2.2 Randomization and treatment period (Visit1-Visit4)

Subjects won't be able to eat or drink anything for eight hours before visit 1, visit 2, visit 3 and visit 4.

Visit 1 (Randomization)

1. Before randomization, the investigator should complete the following actions and collect the relevant data:

- Collect general information:

Demographics data: gender, date of birth, education, insurance
- Retrieving and reviewing the Patient Diary
- Collect the information of clinical assessment such as Serum lipids (TG/non HDL-C/TC/LDL-C), HbA1c , Plasma Glucose (PG), PPG, insulin and C-peptide at fasting and 2h after glucose solution (75g glucose) . Hepatic function (Bilirubin, albumin, liver enzymes), Creatine kinase (CK), Renal function (Serum creatinine, BUN ,eGFR), Routine blood test, Pregnancy test (HCG test for women of childbearing potential only),and ECG. According to the results of the above tests, screen the patients again.
- Eligibility criteria: To verify the participants satisfy all the inclusion criteria and without any exclusion criteria.

2. Randomization.

3. Medical history: Including previous medical history, treatment before screening and other comorbidities.

4. Physical examination: blood pressure, pulse rate, weight, height.

5. Collect the information of Concomitant medications.

6. Collect the information of history of adverse events with statins.

7. Collect physical activity information: Physical activity level by for Measurement of a Person's Habitual Physical Activity (IPAQ)

8. Patients should be guided for medication.

9. Distribute study drugs by groups, patients should start the treatment after the day of randomization

Visit 2 (4 weeks after treatment phase)

1. Collect the information of Concomitant medications.
2. Collect the information of adverse events. If any AE is reported, relevant laboratory test should be collected.
3. Collect the information of clinical assessment such as Serum lipids (TG/non HDL-C/TC/LDL-C), Plasma Glucose (PG), PPG, insulin and C-peptide at fasting and 2h after drinking glucose solution (75g glucose) . Hepatic function (Bilirubin, albumin, liver enzymes), Creatine kinase (CK), Renal function (Serum creatinine, BUN ,eGFR).
4. Collect physical activity information: Physical activity level by for Measurement of a Person's Habitual Physical Activity (IPAQ)
5. Patients should be guided for medication and lifestyle
6. Review of the patient's diary, compliance to study medication
7. Distribute study drugs by groups.
8. Retrieving drugs and log cards

Visit 3 (12 weeks after randomization)

1. Collect the information of Concomitant medications.
2. Collect the information of adverse events. If any AE is reported, relevant laboratory test should be collected.
3. Collect the information of clinical assessment such as Serum lipids (TG/non HDL-C/TC/LDL-C), HbA1c, Plasma Glucose (PG), insulin and C-peptide at fasting and 2 h after drinking glucose solution (75g glucose) .
4. Collect physical activity information: Physical activity level by for Measurement of a Person's Habitual Physical Activity (IPAQ)
5. Patients should be guided for medication and lifestyle
6. Review of the patient's diary, compliance to study medication
7. Distribute study drugs by groups.
8. Retrieving drugs and log cards

Visit 4 (24 weeks after randomization)

1. Collect the information of Concomitant medications.
2. Collect the information of adverse events. If any AE is reported, relevant laboratory test should be collected.
3. Collect the information of clinical assessment such as Serum lipids (TG/non HDL-C/TC/LDL-C), HbA1c , Plasma Glucose (PG), PPG, insulin and C-peptide at fasting and 2h after glucose solution (75g glucose) ,Hepatic

function (Bilirubin, albumin, liver enzymes), Creatine kinase (CK), Renal function(Serum creatinine, BUN ,eGFR), Routine blood test, and ECG.

4. Collect physical activity information: Physical activity level by for Measurement of a Person's Habitual Physical Activity (IPAQ)
5. Patients should be guided for medication and lifestyle
6. Review of the patient's diary, compliance to study medication
7. Retrieving drugs and log cards

4.3 lifestyle modification

Throughout the study, investigators should emphasize the importance of adequate supportive care, such as diet, weight maintenance and physical activity. As guideline recommended, each participant should consume a dietary pattern that emphasizes intake of vegetables, fruits, whole grains, legumes, healthy protein sources(low-fat diary products, low-fat poultry (without the skin), fish/seafood, and nuts), and non tropical vegetable oils; and limits intake of sweets, sugar-sweetened beverages, and red meats. This dietary pattern should be adjusted to appropriate calorie requirements, personal and cultural food preferences, and nutritional therapy for other medical conditions including diabetes. Caloric intake should be adjusted to avoid weight gain, or in overweight/obese patients, to promote weight loss. In general, adults should be advised to engage in aerobic physical activity 3-4 sessions per week, lasting on average 40 minutes per session and involving moderate-to vigorous-intensity physical activity.

4.4 Patient diary

Patient diary will be used to evaluate subject compliance. Patient diary has to be completed by the subject every day in the last one week before the study visit. The diary includes date, dose of medication, time of dosage, daily diet, daily physical activity . (Appendix II)

5 STUDY ASSESSMENTS

5.1 Efficacy Assessments

5.1.1 Primary endpoint

The change value of HbA1c levels from baseline to 24 Weeks or before antidiabetic therapy initiation within 24 weeks.

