5.1.2 Secondary endpoints

The change value of FBG, PPG 2h and HOMA-IR from baseline to 24 Weeks or before antidiabetic therapy initiation within 24 weeks.

The percentage change of LDL-C levels from baseline to 24 Weeks or before antidiabetic therapy initiation within 24 weeks.

The percentage change of non HDL-C levels from baseline to 24 Weeks or before antidiabetic therapy initiation within 24 weeks.

The change value of HbA1c levels from baseline to 12 Weeks or before antidiabetic therapy initiation within 12 weeks.

The change value of FBG, PPG 2h and HOMA-IR from baseline to 12 Weeks or before antidiabetic therapy initiation within 12 weeks.

The percentage change of LDL-C levels from baseline to 12 weeks or before antidiabetic therapy initiation within 12 weeks.

The percentage change of non HDL-C levels from baseline to 24 Weeks or before antidiabetic therapy initiation within 12 weeks.

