8 STATISTICAL ANALYSES

8.1 Sample size estimate

The primary endpoint of the study is the change value of HbA1c levels from baseline to 24 Weeks or before antidiabetic therapy initiation within 24 weeks.

We assume that the HbA1c level doesn't change in XZK group, and an increase of HbA1c level by 0.3% in atorvastatin 20mg group based on findings from Koh K et al. The SD of change of HbA1c level is 1.0% for both treatment.

The sample size of each group of 176 will provide 80% power at a 5% significance level. Considering 10% drop out rate, the total sample size is 392.

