8.3 Definitions of analysis sets

The full analysis set (FAS) includes all randomized subjects who received at least 1 dose of IP (investigational product) and have a non-missing HbA1c value at week 24. This analysis set will be used in both efficacy and safety analyses.

The Completer Analysis Set (CAS) includes subjects in FAS who completed IP and have a non-missing HbA1c value at week 24.

In all analysis sets, unless specified otherwise, subjects will be analyzed according to the ITT principle.

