8.4 Efficacy analysis

8.4.1 The primary endpoints

The change value of HbA1c levels from baseline to 24 Weeks or before antidiabetic therapy initiation within 24 weeks will be analyzed using covariance(ANCOVA) model use the treatment group(XZK, atorvastatin) as the group and the baseline HbA1c as the covariate. The results will be presented as least squares means (lsmeans) with 95% confidence intervals and p-values. Model assumptions will be explored and, if necessary, appropriate transformations or non-parametric analysis techniques will be used. The primary analysis set for this analysis is the full analysis set (FAS).

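### The FAS requires a week-24 HbA1c, which does not match the primary endpoint and, because the same set serves safety, removes treated patients from the adverse-event tables

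*Protocol*

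**What the plan says.** **Endpoint.** Section 5.1.1, repeated in 8.1 and 8.4.1, defines the primary endpoint as "The change value of HbA1c levels from baseline to 24 Weeks or before antidiabetic therapy initiation within 24 weeks". Section 5.1.2 has a parallel secondary endpoint: "The change value of HbA1c levels from baseline to 12 Weeks or before antidiabetic therapy initiation within 12 weeks".

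**Analysis sets.** Section 8.3 builds the FAS from randomized subjects with at least one dose who "have a non-missing HbA1c value at week 24. This analysis set will be used in both efficacy and safety analyses". Section 8.4.1 adds: "The primary analysis set for this analysis is the full analysis set (FAS)". The completer set repeats the week-24 condition, and 8.3 also invokes the ITT principle. Section 8.4.3 tabulates adverse events, including those leading to discontinuation.

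**Schedule.** Table 1 and 4.2.2 place HbA1c at Visit 1 (week 0), Visit 3 (day 85 ±7) and Visit 4 (day 169 ±7). Visit 2 at week 4 lists "Serum lipids (TG/non HDL-C/TC/LDL-C), Plasma Glucose (PG), PPG, insulin and C-peptide at fasting and 2h after drinking glucose solution (75g glucose)", without HbA1c. Visit 3 is the first post-baseline visit to include it: "HbA1c, Plasma Glucose (PG), insulin and C-peptide at fasting and 2 h after drinking glucose solution (75g glucose)". No section requires an HbA1c when antidiabetic therapy is started.

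**Follow-up and missing data.** Section 3.8 wants HbA1c collected to the end of the study, even off study drug. Section 3.9 states: "We define loss to follow-up as incomplete ascertainment of the primary outcome for participants randomized in the trial". Section 8.2 applies no imputation unless specified. Section 8.1 plans 176 per group and ends: "Considering 10% drop out rate, the total sample size is 392".

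**The concern.** For a therapy starter, FAS membership depends on a measurement that the endpoint does not use. A subject who starts after Visit 3 and misses week 24 is dropped although the endpoint value is known. A starter who attends week 24 is admitted because of a value that is then set aside.

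The same condition governs safety. Subjects who took study drug, had an adverse event, left and gave no week-24 sample would not be counted. These are the subjects whom a table of events leading to discontinuation is meant to show.

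The schedule adds a smaller problem. For a start before Visit 3 the only planned pre-therapy HbA1c is baseline. The change is then either zero by construction or missing, and 5.1.1 does not say which.

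**Working it through.** **1. The plan's own figure.** Inputs from 8.1: difference 0.3, SD 1.0, 5% level (two-sided assumed; it reproduces the stated n), 176 per group, 10% dropout.
- Standard error: 1.0 × √(2/176) = 0.1066. Standardized difference: 0.3/0.1066 = 2.81. Two-sample t-test power: 80.1%.
- Total: 2 × 176 = 352; 352/0.90 = 391.1, so 392 (196 per arm).

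The stated sample size reproduces and is not in question.

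**2. Safety loss.** 392 − 352 = 40 subjects. This is an upper figure at the planned dropout: some dropouts may still give a week-24 sample under 3.8, and any subject never dosed would be outside a safety set anyway. No assumption about therapy starts is needed.

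**3. Known endpoints dropped from the FAS.** The protocol gives no rate of antidiabetic starts. Assume that 2% or 10% start between weeks 12 and 24, and that 10% of these miss week 24 (the planned dropout rate).
- 392 × 0.02 × 0.10 = 0.8
- 392 × 0.10 × 0.10 = 3.9

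That is about 1 to 4 subjects.

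**4. Starts before Visit 3.** Let p be the share of early starters in an arm and m their mean change, both assumed. The arm mean μ is 0.3 (atorvastatin) or 0 (XZK), with total variance 1.
- Mean of the other subjects: r = (μ − p·m)/(1 − p). Variance within the two groups: w = 1 − p(1 − p)(m − r)².
- Zero reading: mean (1 − p)·r, variance (1 − p)·w + p(1 − p)·r², n = 176. The difference becomes 0.3 − m(p_A − p_X).
- Missing reading: mean r, variance w, n = 176(1 − p), or n = 176 if early starters are absorbed in the 10% dropout allowance.

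Example, 10% vs 4% with m = 0.8:
- Zero reading: difference 0.3 − 0.8 × 0.06 = 0.252; variances 0.880 and 0.934; standard error √(1.815/176) = 0.1015; power 69.7%.
- Missing reading: r = (0.3 − 0.08)/0.90 = 0.244 and r = −0.032/0.96 = −0.033; difference 0.278; power 71.9%, or 75.0% if absorbed.

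Power (Welch t-test, two-sided 5%):

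| Early starters, atorvastatin vs XZK | Zero, m = 0.1 | Zero, m = 0.3 | Zero, m = 0.8 | Missing, m = 0.3 | Missing, m = 0.8 | Absorbed, m = 0.8 |
|---|---|---|---|---|---|---|
| 1% vs 0.5% | 0.803 | 0.800 | 0.795 | 0.802 | 0.797 | 0.800 |
| 2% vs 1% | 0.804 | 0.799 | 0.788 | 0.803 | 0.792 | 0.798 |
| 5% vs 2% | 0.807 | 0.791 | 0.753 | 0.803 | 0.765 | 0.780 |
| 10% vs 4% | 0.813 | 0.780 | 0.697 | 0.805 | 0.719 | 0.750 |

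In the first two rows, at m = 0.3 or 0.8, the range is 78.8% to 80.3%. A fall to about 70% needs both the highest assumed rates and a mean rise of 0.8 among subjects who start before week 12.

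**The case against.** The strongest reply is that few subjects are affected. Section 3.8 asks for HbA1c to study end, so a known endpoint is lost only when a late starter also misses week 24. Sections 3.6 and 7.7.1 prohibit antidiabetic drugs, so starts should be uncommon. This stands and keeps the starter issue minor.

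A second reply is that the choice of pre-therapy value, and the handling of subjects with baseline only, can be left to the SAP, which is not shown. This stands in part. But the FAS and the endpoint are both fixed in the protocol and do not match, and no SAP can recover a sample that was never drawn. The instruction in 4.2.2 to collect relevant laboratory tests when an adverse event is reported could yield an unscheduled HbA1c, but it does not require one, and 6.9 limits which laboratory changes count as adverse events.

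A reader might infer that 3.6 and 7.7.1 contradict 5.1.1, because one forbids what the other foresees. The text does not support that: a prohibition can stand beside a rule for analysing departures from it.

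None of these replies answers the safety point, which does not depend on antidiabetic starts.

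**Conclusion.** The week-24 HbA1c condition in 8.3 is wrong as written and should be corrected, chiefly because it also defines the safety population. Up to 40 of 392 subjects would leave the adverse-event tables at the planned 10% dropout. For efficacy, the mismatch with 5.1.1 would discard about 1 to 4 known endpoint values under the assumed rates.

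The absence of a planned post-baseline HbA1c before Visit 3 is real but minor. It applies equally to the 12-week HbA1c endpoint; the glucose, insulin-based and lipid endpoints do have a week-4 measurement.

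A reader might infer a serious loss of power or a false finding of superiority. The documents support neither. They give no starter rate, and power barely moves at 1% to 2% early starters on atorvastatin. If starts are more frequent on atorvastatin and starters' HbA1c rises on average, the zero reading shrinks the difference rather than creating one.

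**What to change.** 1. In 8.3, define a safety set of every subject who took at least one dose, with no HbA1c condition.
2. In 8.3, remove the week-24 condition from the FAS, leaving all randomized and dosed subjects, analysed as randomized. Those with an endpoint value under 5.1.1 contribute it; handling of the rest is left to the SAP. Keep the week-24 condition for the completer set only. Requiring a non-missing endpoint instead could remove early starters who are in the FAS today through their week-24 value.
3. In 5.1.1, state that the pre-therapy value is the last post-baseline HbA1c sampled before the first antidiabetic dose. Judge this by actual sample and dose dates, not nominal weeks, because visits have a ±7-day window. Apply the same rule to the 12-week HbA1c endpoint in 5.1.2.
4. In Table 1 and 4.2.2, add an HbA1c on blood taken before the first antidiabetic dose when no post-baseline HbA1c exists. This concerns measurement only, not whether or when therapy starts.
5. As a sensitivity analysis, analyse the observed week-24 HbA1c in all FAS subjects who have one. Section 3.8 already asks for these data.

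**Cost.** Mostly wording. Extra assays, at assumed early-start rates: 196 × (0.02 + 0.01) = 5.9, about 6; or 196 × (0.10 + 0.04) = 27.4, about 27. The sample size is unchanged. The downside is that an early pre-therapy value reflects less than 24 weeks of exposure, which is why item 5 should be shown beside the primary result.

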8.2 General consideration

Analyses will be performed by SAS 9.4 statistical software. Descriptive statistics will be calculated, including n, means, standard deviations, medians, and interquartile ranges for continuous variables and frequency counts and percentages for categorical variables. Percentage will be calculated based on non-missing data unless otherwise specified. Data will be examined for skewness, outliers. Transformations will be undertaken as needed.

Missing data will be assumed missing at random or missing completely at random. In general, no imputation will be applied unless otherwise specified.

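### The primary endpoint can call for an HbA1c from before antidiabetic start, but no such sample is required, and the FAS rule can exclude a participant who has one

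*Protocol*

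**What the plan says.** Sections 3.6 and 7.7.1 of the protocol prohibit antidiabetic agents during the study. The primary endpoint in 5.1.1 nevertheless provides for their use: "The change value of HbA1c levels from baseline to 24 Weeks or before antidiabetic therapy initiation within 24 weeks". Sections 8.1 and 8.4.1 repeat the definition, and 5.1.2 has a week-12 counterpart: "The change value of HbA1c levels from baseline to 12 Weeks or before antidiabetic therapy initiation within 12 weeks".

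Table 1 marks HbA1c at Visits 1, 3 and 4 only. The visit lists in 4.2.2 agree. Visit 2 (week 4) collects "Serum lipids (TG/non HDL-C/TC/LDL-C), Plasma Glucose (PG), PPG, insulin and C-peptide at fasting and 2h after drinking glucose solution", without HbA1c. Visit 3 (week 12) collects "Serum lipids (TG/non HDL-C/TC/LDL-C), HbA1c, Plasma Glucose (PG), insulin and C-peptide at fasting and 2 h after drinking glucose solution". No section ties an HbA1c draw to the start of an antidiabetic drug.

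Section 8.4.1 makes the FAS the primary analysis set. Under 8.3 its members are randomized subjects who "received at least 1 dose of IP (investigational product) and have a non-missing HbA1c value at week 24". On missing values, 8.2 says: "In general, no imputation will be applied unless otherwise specified". On follow-up, 3.8 asks for HbA1c to the end of the study even after study drug is stopped, and 3.9 says: "We define loss to follow-up as incomplete ascertainment of the primary outcome for participants randomized in the trial".

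**The concern.** The endpoint, the sampling schedule and the analysis set do not fit together for participants who start an antidiabetic drug. The endpoint may need a value that nobody is told to collect, and the FAS tests for a different value from the one the endpoint uses.

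These participants matter because their glycaemia worsened enough to be treated, and glycaemic worsening is the trial's question. Treatment is open-label, so the decision to start could differ between arms. A sample that was never drawn cannot be recovered at analysis, so the sampling rule belongs in the protocol and not in a later analysis plan.

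**Working it through.** **1. What the schedule yields for a starter** (visit days and windows from Table 1)

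- Start before the Visit 3 draw: the only scheduled pre-initiation HbA1c is baseline. The change is zero if baseline is carried forward, and otherwise undefined. No post-baseline HbA1c is planned in the first 85 of 169 days (85/169 = 50%).
- Start after the Visit 3 draw: the week-12 value serves. It can be up to 169 − 85 = 84 days old at the start, or (169 + 7) − (85 − 7) = 98 days at the window limits. A start prompted by Visit 3 results would have a fresh value.
- Week-12 HbA1c endpoint: Visit 3 may take place from day 85 − 7 = 78, and 12 weeks is 84 days. Only someone sampled early in the window who starts in the few days left has a post-baseline pre-initiation value. Nearly all starters within 12 weeks have baseline alone.

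**2. FAS membership against endpoint availability**

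| Starter | Endpoint value under 5.1.1 | In FAS under 8.3 |
|---|---|---|
| Before Visit 3 draw, week-24 sample taken | baseline only (zero or undefined) | yes |
| After Visit 3 draw, week-24 sample taken | week-12 value | yes |
| After Visit 3 draw, no week-24 sample | week-12 value | **no** |

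The last row is the direct conflict. That participant has the primary outcome, so 3.9 does not count them as lost to follow-up, yet 8.3 excludes them from the primary analysis.

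**3. The plan's own figure**

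From 8.1: difference 0.3, SD 1.0, 5% significance (two-sided assumed, as sidedness is not stated), 80% power. The two-sample t-test gives 175.4, so 176 per group, and 176 per group has 80.1% power. For dropout, 176/0.9 = 195.6, rounded up to 196, and 2 × 196 = 392. Both stated figures reproduce.

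**4. Illustration of size**

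The protocol gives no start rate. Assume k = 5 to 10 excess starters in one arm and SD held at 1.0. Let r be their mean HbA1c rise up to the start: 0.2 to 0.5 for early starters, and 0.5 to 1.0 for those with a week-12 value. All k and r are assumptions.

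- Early starters scored as zero, shift = k·r/176:
  - 5 × 0.2/176 = 0.0057 (1.9% of 0.3)
  - 10 × 0.5/176 = 0.0284 (9.5% of 0.3)
  - On atorvastatin the contrast shrinks and power is 78.6% to 71.9%. On XZK the contrast grows by the same amount.
- Early starters on atorvastatin treated as missing, arm mean = (176 × 0.3 − k·r)/(176 − k):
  - k = 10, r = 0.2: 50.8/166 = 0.3060 (shift +0.006), power 80.5%
  - k = 10, r = 0.5: 47.8/166 = 0.2880 (shift −0.012), power 75.6%
- FAS exclusion on atorvastatin, with 176 remaining, arm mean = ((176 + k) × 0.3 − k·r)/176:
  - k = 5, r = 0.5: 51.8/176 = 0.2943 (shift −0.006), power 78.6%
  - k = 10, r = 1.0: 45.8/176 = 0.2602 (shift −0.040), power 68.2%
- FAS exclusion on XZK, contrast inflated by k·r/176:
  - 5 × 0.5/176 = 0.0142 (4.7% of 0.3); rejection rate with no true difference 5.2%
  - 10 × 1.0/176 = 0.0568 (18.9% of 0.3); rejection rate with no true difference 8.3%

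Equal numbers of starters with equal rises in both arms give a shift of about zero. The planned dropout allowance is 392 − 352 = 40, about 20 per arm, so ten excluded starters would be half of one arm's allowance.

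**The case against.** The case for leaving the text alone is substantial.

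- Antidiabetic drugs are prohibited and people with diabetes are excluded at entry, so starts within 24 weeks are protocol deviations and may be few. This stands as a limit on size. It does not remove the mismatch, because the endpoint itself provides for starts and 3.7.1 does not list them as a reason to stop study drug.
- Section 3.8 pursues the week-24 HbA1c even off study drug, so the FAS conflict reaches only starters who also miss that sample. This stands. A reader might infer that 8.3 removes starters as a class, and it does not. Nor is the rule confined to starters: it drops anyone without a week-24 value, which is a wider question.
- Section 4.2.2 asks for relevant laboratory tests when an adverse event is reported. This is a partial safeguard at best. It names neither HbA1c nor timing before the first antidiabetic dose, and 6.9 limits which laboratory changes count as adverse events.
- Whether a baseline-only case scores zero or missing, and whether to add a supportive analysis of week-24 HbA1c regardless of antidiabetic use, are commonly left to the SAP. This also stands, and neither is held against the protocol here.

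Two stronger readings should be resisted. One is that the week-12 clause can never select a post-baseline value. The ±7-day window leaves a few days in which it can. The other is that the trial loses much of its power. If 10% of the atorvastatin arm and none of the XZK arm started before week 12, with a mean rise of 1.0 scored as zero, the contrast would be 0.3 − 0.10 × 1.0 = 0.20 and power about 47%. Nothing in the protocol supports such an imbalance.

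**Conclusion.** The point holds in a limited form. The endpoint relies on a pre-initiation HbA1c that the protocol does not secure, and 8.3 conflicts with 5.1.1 for a starter who has a week-12 endpoint value and no week-24 sample. Both follow from the text without assumptions.

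The effect on the result is not established. Under the assumed imbalance of 5 to 10 starters, the contrast moves by 0.006 to about 0.03 when early starters score zero, and by 0.006 to about 0.06 across the FAS-exclusion cases. A reader might infer a bias in favour of one drug, but the documents do not support a direction. Excess starters on atorvastatin would mostly dilute the difference, and excess starters on XZK would inflate it where they are scored as zero or excluded from the FAS. Rare or balanced starts leave it essentially unchanged. The reason to act is that the remedy is cheap and an undrawn sample is lost for good.

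**What to change.** 1. In 3.6 and 7.7.1, keep the prohibition and add that, if an antidiabetic drug is nevertheless to be started, HbA1c is drawn before its first dose where clinically feasible, by the same rule in both arms.
2. In 8.3, let a post-baseline pre-initiation HbA1c that is valid under 5.1.1 qualify a participant for the FAS, as an alternative to the week-24 value.

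The cost is an occasional unscheduled blood sample and two sentences of text. No change to the sample size or the ANCOVA model is needed. A pre-dose sample records only the change up to the start, and how to handle what follows can be left to the SAP.
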